North Star Ambulatory Assessment: the 17 items of the NSAA, ranging from standing to running 10 meters, will be graded using the standard score card with each assessment rated as 0 – unable to achieve independently, 1 – modified method but achieves goal independent of physical assistance from another, or 2 – normal with no obvious modification of activity.

Muscle strength: using HHM, the muscle strength of knee extensor and elbow flexor will be measured following standardized procedures; bilateral assessments will be done, and 3 measurements will be recorded from each muscle group on each side.

Quality of Life (QoL): the QoL will be measured via the American Academy of Orthopaedic Surgeons Pediatric Musculoskeletal Function Instrument, also referred to as PODCI. The PODCI will be administered to the parent/legal guardian of subjects. The PODCI is comprised of several dimensions that assess upper extremity function, transfers and mobility, physical function and sports, comfort/pain (pain-free), and happiness. There is also a scale for global functioning, which is a combination of the 3 function subscales and comfort.

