4.3.2 Paediatric Outcomes Data Collection Instrument (PODCI) Scores

The PODCI quality of life questionnaire can either be completed by the subject's parent or the subject themselves. A total of five subscales (upper extremity function; transfer and basic mobility; sports and physical functioning; pain/comfort and happiness) and one global function scale can be calculated from the questionnaire.

Summary statistics for the raw scores and standardised scores, together with the change from baseline over time for each subscale included in the PODCI assessment, as well as for the standardised scores of the global function scale will be presented by treatment group. These tables will be produced separately for assessments completed by parents and for assessments completed by the subjects themselves. The endpoints of interest will be the change from baseline to 18 months in the standardised scores for each subscale and the global function scale, as completed by the parent and the subject.

Details of the items included in each of the subscales, as well as the calculations to be applied in order to derive the raw and standardised scores, are included in Appendix 7.4.

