2 CHANGES TO THE FINAL SAP

2.1 Change 1

According to the SAP Sections 4.3.2 and 4.4.2, for the Paediatric Outcomes Data Collection Instrument (PODCI) endpoint, change from baseline over time for raw and standardised subscale scores are to be presented and analysed separately for 'parent' or 'self' evaluator. However, on review of the data following database lock and prior to unblinding, it was confirmed that there are a number of cases where a subject has completed a mixture of questionnaires by different evaluators from screening to end of study. Unfortunately, the SAP does not cover this type of scenario.

Italfarmaco and Veristat discussed possible solutions with consideration that a subject will only have a baseline questionnaire completed for one type of evaluator even though this may differ from the evaluator for the post-baseline visit. In order to avoid limitation to only subjects with consistent evaluator across baseline and post-baseline for calculating change from baseline values, a pooled approach has been identified. This was supported by the assumption that scores from questionnaires completed by 'self' where the subject is <10 years of age are considered not fully reliable. However, scores from questionnaires completed by 'self' where the subject is >=10 years old can be considered reliable and comparable to scores from questionnaires completed by 'parent'.

In the data we will have a mixture of questionnaires completed by: 'Parent', 'Self >=10 years', 'Self <10 years', 'Missing' (where missing evaluator applies to completely imputed results where the assessment/visit was not done). Therefore, the approach will be as follows.

Questionnaires will be divided into two groups based on the type of evaluator:

- Group 1: 'Parent' + ('Self' >=10 years old)
- Group 2: 'Missing' + ('Self' <10 years old)

Group 1 non-missing subscale scores will remain unchanged. Group 1 missing subscale scores will be imputed as described in the SAP Sections 4.4.4.1, 4.4.4.2 and 7.5.8 using the approach for Class 1 missing data based on Group 1 non-missing results (for the respective subscale, visit, treatment, concomitant steroid and target/off-target group).

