Group 2 subscale scores (both non-missing or missing scores) will be replaced with imputed values using the same approach for Class 1 missing data but also based on Group 1 non-missing results (for the respective subscale, visit, treatment, concomitant steroid and target/off-target group), rather than Group 2 non-missing results.

All values (Group 1 and Group 2 non-missing and imputed values) will then be analysed together as equivalent measures, i.e., all are included in calculation of change from baseline and summaries/analyses. The analysis tables will be presented based on these values without distinction between different evaluators. The amended table, figure and listing (TFL) shells for these presentations are supplied in the separate document 'TFL Shells Addendum 1'. These replace the following equivalent planned outputs in the TFL Shells Final 4.0: Tables 14.2.8.1.1 to 14.2.8.5.6 and Listings 16.2.6.8.1 to 16.2.6.8.4.

Reason for the change

As detailed above, this change has been implemented as the SAP defined approach did not allow for the mixture of questionnaires completed by different evaluators per subject as collected in the data.

2.2 Change 2

Section 7.4.1 of the SAP (PODCI Completed by Parent) includes the following instruction when describing the required derivations for some of subscale scores on the parent completed questionnaires: "any item rated "5" (Too young for this activity) is considered missing and is not added to the scale".

It was noted that for some questions on the parent completed questionnaire, the response indicating that the subject was too young for the activity is given a different number, for example '6' rather than '5'. In addition, there are some questions where the response is phrased slightly differently, for example: "Child is too young". Affected questions are questions 10 to 14 used for the 'Happiness' subscale.

To accommodate these differences, the approach was therefore corrected to consider any item as missing for subscale calculation if the text response contains the phrase 'too young' (regardless of the number of the response or exact phrasing of the full response). This was agreed to be the intention of the SAP instructions.

Reason for the change

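### SAP Addendum 1 pools parent and self-completed PODCI scores as equivalent on an untested assumption, and no planned analysis table shows change with the same respondent at both visits

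*SAP*

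**What the plan says.** Protocol 10.2 names one respondent: "The PODCI will be administered to the parent/legal guardian of subjects". SAP 4.3.2 allows either the parent or the boy to complete the questionnaire, but keeps the two apart: "These tables will be produced separately for assessments completed by parents and for assessments completed by the subjects themselves". SAP 4.4.2 carries that separation into the ANCOVA of the standardised scores. The PODCI model has baseline score, age at first dose, treatment and steroid stratum, and no term for respondent.

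Addendum 1, section 2.1 (Change 1) departs from this. The mixture of evaluators came to light "on review of the data following database lock and prior to unblinding". Each boy has a baseline questionnaire from only one kind of evaluator, "even though this may differ from the evaluator for the post-baseline visit". The addendum gives its reason for pooling: "In order to avoid limitation to only subjects with consistent evaluator across baseline and post-baseline for calculating change from baseline values".

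The new rule forms two groups:
- **Group 1:** parent scores and self scores at age 10 or over. These stand as recorded, on the assumption that the self scores "can be considered reliable and comparable to scores from questionnaires completed by 'parent".
- **Group 2:** self scores under age 10, and records with no evaluator. These are overwritten with Group 1 means.

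All values "will then be analysed together as equivalent measures, i.e., all are included in calculation of change from baseline and summaries/analyses". On presentation: "The analysis tables will be presented based on these values without distinction between different evaluators". The new outputs take the place of the planned PODCI tables and listings.

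**The concern.** Take a boy whose parent answered at screening and who answered for himself, aged 10 or over, at month 18. His change score is his own rating minus his parent's. Any systematic disagreement between the two is counted as change, no model term separates it out, and the tables that kept respondents apart have been replaced.

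Comparability therefore underlies the whole pooled PODCI result, yet it is stated without data or citation and no check on it is specified. Quality of life is a secondary objective (Protocol 5.1.2), and PODCI is the only quality-of-life test in the schedule (Protocol Table 6). From the analysis tables a reader could not tell whether the pooled result agrees with parent report, which is the measure that Protocol 10.2 describes.

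**Working it through.** The plan gives no figure to reproduce. The check sets the scoring rules side by side and then sizes the effect under stated assumptions.

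**1. Are the two forms scored alike?** For sports and physical function, SAP 7.4.1.3 sets parent items Q36, Q44 and Q52 to missing when the item is scored 4 and either of two follow-up questions equals 1. In SAP 7.4.2.3 the self-form items Q36, Q43 and Q50 each have a single follow-up question (the one for Q50 is corrected in Addendum section 2.3). The standardised score is 100 × (4 − mean of items)/3, over 12 items.

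Take one item scored 4 and the other eleven averaging 2:
- Item dropped: 100 × (4 − 2)/3 = 66.7.
- Item counted: mean = (11 × 2 + 4)/12 = 2.167, so 100 × (4 − 2.167)/3 = 61.1.
- Difference: −5.6 points from the same answers.

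This assumes that the extra parent-form trigger has no counterpart on the self form. The SAP does not say what that question asks or how often it would apply. The example shows that the scoring rules differ; it does not estimate the parent–self gap.

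**2. Added noise.** From the documents: 110 boys randomised 2:1, so about 73 and 37. Assumed, because the documents give none of them: score SD 15, baseline correlation 0.6, respondent gap D of 5 to 15 points, and share switching s of 10 to 30%, all in one direction and equally in both arms.

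- Residual SD = 15 × √(1 − 0.6²) = 12, so residual variance is 144.
- SE without switching = 12 × √(1/73 + 1/37) = 2.42 points.
- SE ratio with switching = √((144 + s(1 − s)D²)/144).

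| s | D = 5 | D = 10 | D = 15 |
|---|---|---|---|
| 10% | 1.01 | 1.03 | 1.07 |
| 20% | 1.01 | 1.05 | 1.12 |
| 30% | 1.02 | 1.07 | 1.15 |

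The rise is about 1 to 15%, and 5% at the central case (10 points, 20%).

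**3. Chance imbalance in switching is the same effect.** Its typical size is D × √(s(1 − s)(1/73 + 1/37)). At D = 10 and s = 0.2 this is 0.81 points. Then √(2.42² + 0.81²) = 2.55, and 2.55/2.42 = 1.05, which is the 5% already in the table.

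**4. Bias.** The treatment difference moves by (share switching on givinostat − share on placebo) × D. With equal shares it moves by 0. At 30% versus 10% it moves by 0.2 × 5 = 1 point to 0.2 × 15 = 3 points.

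**The case against.** The strongest reply is that this is ordinary residual variance in a double-blind randomised comparison, on an endpoint reported with nominal p-values (SAP 4.3, Protocol 13.7.3). The ANCOVA's own confidence interval already reflects it. That stands, and it limits how much the point matters.

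Age also helps. Self scores under 10 are overwritten, so a recorded parent-to-self switch by month 18 needs a boy aged about 8.5 or more at first dose (10 − 1.5 years), and age at first dose is a covariate. This stands in part. A single age slope absorbs some of the shift, but it cannot separate two boys of the same age of whom only one changed respondent.

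The sponsor considered a same-evaluator restriction and declined it so as not to lose boys. That is a fair reason for keeping the pooled analysis as the main one. It is no reason to leave out a sensitivity analysis.

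A reader might infer two stronger things that the documents do not support:
- **That pooling was chosen with results in view.** The addendum places the finding before unblinding, and its introduction lists a signed PODCI file note among those agreed before unblinding.
- **That the evaluator has vanished from every output.** The amended shells and the file note are not among the documents. Only the analysis tables are known to drop the distinction; the listings may still show it.

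**Conclusion.** The point holds at modest size. For boys who changed respondent, the pooled change score confounds respondent with change, the equivalence assumption is openly stated but untested, and no planned analysis table would test it. Primary and key secondary conclusions are unaffected.

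The main cost is lost precision, under inputs that are all assumed; the addendum gives no count of switchers, only that there were a number of cases. A reader might infer that the PODCI treatment effect is biased, or that chance imbalance in switching adds error beyond the wider standard error. Neither follows. Bias would need switching to differ between arms, of which the documents give no evidence, and the imbalance is already inside the standard error. The change is still worth making, because it uses data already collected and lets the trial check the assumption on which its quality-of-life result rests.

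**What to change.** In Addendum 2.1, keep the pooled analysis and add beside it:

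1. A sensitivity ANCOVA and table limited to boys with observed parent questionnaires at both screening and month 18, labelled as a subset defined after randomisation, with counts of respondent switches by arm and visit.
2. Screening respondent as a class factor in the pooled PODCI ANCOVA, with levels parent, self, and a separate level for overwritten or missing baseline scores.

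Do not adjust for month-18 respondent. It arises after randomisation and could itself be affected by treatment, and a simple parent-or-self factor has no level for overwritten or missing records.

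The cost is addendum wording, one extra table set with the counts, and one or two degrees of freedom. The sensitivity analysis will have a smaller, selected N, so it should be read for consistency with the pooled result and not as a replacement for it.
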